**January 21, 2021**

## PROTOCOL STUDY

Clinical trial in adults hospitalized patients in Respiratory Intermediate Care Unit (RICU) of *University Germans Trias i Pujol Hospital*.

### Admission in RICU

The patient is included in the study after signing informed consent. In this moment, a blood sample is obtained and vital constants of patient like respiratory rate (RR), heart rate (HR), EKG signal, Oxygen Saturation (SaO2) and blood pressure start to be monitored continuously. Barthel index and dyspnoea grade of MRC scale are registered.

### Standard support with Oxygen High Flow (OHF)

#### Day 1

All patients start respiratory support with oxygen high flow system (AIRVO2 or V60 plus), if it doesn't exist contraindications.

Initial parameters: Temperature 34-37°C, flow 30 l/min and FiO2 100%. Then the flow will be progressively increased until the respiratory rate is less than 35, and the FiO2 will be progressively reduced until the minimum concentration to maintain SaO2 greater than 96%. Arterial blood gas analyses and record of vital constants will be performed at 1h, 4h, 6h and 12h after starting high flow therapy.

#### Day 2

24h after starting high flow therapy a new arterial blood gas analyses and record clinical parameters will be performed. If the therapy parameters like FiO2 or flow have been modified it will also be recorded.

#### Day 3

48h after starting high flow therapy control includes arterial gasometry, blood analyses and record clinical parameters, vital constants and therapy parameters.

#### Last day of therapy

Control includes blood analyses and record clinical parameters, vital constants and therapy parameters.

#### Completion criteria to treatment with OHF:

- Respiratory improvement that it leaves to change a conventional oxygen system.
- Lack of tolerance of oxygen high flow system.
- Worsening of respiratory failure defined by a sustained increase in respiratory rate above 30, SaO2 < 90% and distress.
- Death of the patient.

## **Treatment with non-invasive ventilation (CPAP or BiPAP)**

### **Interventional group**

#### **Day 1**

Patients with lack of tolerance to OHF or worsening of respiratory failure with oxygen high flow support are switched to treatment with non-invasive ventilation. Patients are randomized to CPAP or BiPAP ventilatory mode.

The treatment duration is at least 18 hours a day. Initial pressure is 8-10 cmH2O in CPAP group and 16/10 cmH2O in BiPAP group, although it will be increased progressively (from 10 to 12 or 15 cmH2O in cpap group and from 16/10 to 18/12, 20/15 and 22/16 in BiPAP group) until the respiratory rate is lower than 30, and SaO2 > 93%. Initial FiO2 is 100% in both groups, and it will be progressively reduced until the minimum concentration to maintain SaO2 greater than 96%.

Arterial blood gas analyses and record of vital constants will be performed at 1h, 4h, 6h and 12h after starting high flow therapy specifying ventilation parameters.

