## **STADISTICS ANALYSIS**

A part of analysis is carried out using IBM SPSS 25.0 software (SPSS, Chicago, Ill) and the other part by Butler Scientifcs, an external statistical company.

Qualitative variables are expressed as a percentage and are compared using a chi-square study. The quantitative ones are expressed as means or medians with interquartile range and statistical studies are carried out using parametric and non-parametric tests. Demographic and clinical variables are analysed at admission, while analytical, blood gas variables and vital signs are analysed in each of the controls comparing non failure of high flow therapy group with non-invasive ventilation group (CPAP/BIPAP). The same analyses are performed between the CPAP and BIPAP treatment subgroup. A predictive model of OHF failure and non-invasive ventilation failure will be developed using logistic regression or multivariate Cox regression, depending on the case.

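### The randomised CPAP versus BiPAP comparison is planned without covariate adjustment, giving up precision available from values recorded on the last OHF day

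*Combined protocol and SAP*

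**What the plan says.** In the non-invasive ventilation section (Interventional group, Day 1), two routes lead into the randomised comparison: "Patients with lack of tolerance to OHF or worsening of respiratory failure with oxygen high flow support are switched to treatment with non-invasive ventilation". Then: "Patients are randomized to CPAP or BiPAP ventilatory mode". No allocation ratio or stratification factor is given.

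The two routes match two of the completion criteria for OHF. One is "Lack of tolerance of oxygen high flow system". The other begins "Worsening of respiratory failure defined by a sustained increase in respiratory rate above 30" and adds low saturation and distress.

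The statistics section sets chi-square for qualitative variables and parametric or non-parametric tests for quantitative ones, first for patients who did not fail OHF against those who went on to ventilation. For the randomised arms it adds only: "The same analyses are performed between the CPAP and BIPAP treatment subgroup". The one multivariable analysis is a predictive model of OHF failure and of ventilation failure. Its covariates are not listed and ventilatory mode is not named as a term.

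On data available before ventilation, the OHF section says of the last day of therapy: "Control includes blood analyses and record clinical parameters, vital constants and therapy parameters". No arterial gas is listed for that day. The last scheduled OHF gas is at 48 h: "48h after starting high flow therapy control includes arterial gasometry, blood analyses and record clinical parameters, vital constants and therapy parameters".

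**The concern.** CPAP versus BiPAP is the only comparison in this trial protected by randomisation. Patients enter it in differing condition: some were deteriorating by defined respiratory criteria, while others could not tolerate the device and need not have met any of them. Physiological values before ventilation may well predict what happens on ventilation. A plain two-group test leaves that predictable variation in the error term, so confidence intervals are wider than they need be, and any chance imbalance between arms stays in the single estimate obtained. In a single-unit study that could be small, this loss matters most for the one result that can be read causally.

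**Working it through.** **Nothing to reproduce.** The documents state no sample size, power, effect size, event rate or primary endpoint. Every input below is an assumption, shown over a range.

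**1. Continuous outcomes.** With a linear model containing arm and the pre-ventilation value of the same variable, the variance of the arm difference is multiplied by 1 − ρ², where ρ is the correlation between that value and the outcome. For illustration: a true difference of 0.5 SD, two-sided 5% level, 1:1 allocation.

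Patients per arm for 80% power without adjustment: 2 × (1.960 + 0.842)² / 0.5² = 62.8, rounded up to 63. With adjustment, 62.8 is multiplied by 1 − ρ².

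| ρ | Variance factor | Variance saved | n per arm, 80% power | Power at 40 per arm |
|---|---|---|---|---|
| none used | 1.00 | – | 63 | 60.9% |
| 0.3 | 0.91 | 9% | 58 | 65.0% |
| 0.5 | 0.75 | 25% | 48 | 73.3% |
| 0.7 | 0.51 | 49% | 33 | 87.9% |

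At ρ = 0.5, 1/0.75 = 1.33, so leaving the covariate out costs the same precision as losing a quarter of the patients.

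**2. Binary failure of ventilation.** 1,500 trials were simulated per scenario, with 70% entering for worsening (log-odds 1.0 above intolerance), one standardised continuous covariate (log-odds 0.7 or 1.2 per SD) and a treatment log-odds of −0.9. The unadjusted risk difference was compared with one standardised from a logistic model containing arm, entry reason and the continuous covariate.

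| n per arm | Covariate log-odds | Mean difference, unadjusted / adjusted | Variance ratio | Power, unadjusted / adjusted |
|---|---|---|---|---|
| 40 | 0.7 | −0.189 / −0.190 | 0.894 | 42.5% / 44.9% |
| 40 | 1.2 | −0.169 / −0.167 | 0.736 | 33.5% / 37.9% |
| 80 | 0.7 | −0.188 / −0.189 | 0.899 | 68.2% / 74.2% |
| 80 | 1.2 | −0.168 / −0.168 | 0.792 | 58.7% / 69.5% |

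The means agree, which confirms that the unadjusted estimate is not biased on average. These gains assume that entry reason is available to the model.

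**3. Entry reason alone.** Assume 30% enter for intolerance, with failure risks of 20% (intolerance) and 50% (worsening).

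- SD of the between-arm difference in that share = √(2 × 0.3 × 0.7 / n) = 0.145, 0.102 and 0.084 at 20, 40 and 60 per arm. Exact binomial probabilities of a difference of 10 points or more are 60%, 39% and 27%.
- Shift in the risk difference for a 10-point imbalance = 0.10 × (0.50 − 0.20) = 3 points. For risk gaps of 20 to 40 points it is 2 to 4 points.
- Overall risk = 0.3 × 0.20 + 0.7 × 0.50 = 0.41. Standard error at 40 per arm = √(2 × 0.41 × 0.59 / 40) = 0.110. The 3-point shift is 0.03 / 0.110 = 0.27 standard errors.
- Share of outcome variance explained by reason = 0.3 × 0.7 × 0.30² / (0.41 × 0.59) = 0.078. Adjusting for reason alone narrows the interval by about 1 − √0.922 = 4%.

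Imbalance in entry reason is therefore likely but modest in effect. Under these inputs, most of the gain would come from the physiological values.

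**The case against.** The strongest reply is that the planned tests are valid. Randomisation keeps the unadjusted difference unbiased on average, and its confidence interval already allows for chance imbalance. That stands. A reader might infer that the comparison is biased because two kinds of patient are pooled; the documents do not support this, since both kinds are randomised between the same two modes.

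Three other stronger readings also fail.

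- **That the reason for leaving OHF is already recorded.** It must be known at the switch, because it triggers the switch, but no section makes it a data item. Nor are the two criteria stated to be mutually exclusive.
- **That admission is the only baseline analysed.** The phrase "Demographic and clinical variables are analysed at admission" covers only those variables. The same sentence has laboratory values, blood gases and vital signs analysed at each control, so a by-arm description of the last OHF control is arguably already planned. Describing the arms at that control is still not adjusting for it.
- **That the change is free because every value exists.** No gas is listed for the last OHF day, so for a patient who switches after 48 h the latest scheduled gas may be old. The last-day control is also not said to be taken immediately before the switch.

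A large model would be unwise. At 41% failure, 20 to 40 per arm gives 0.41 × 40 = 16 to 0.41 × 80 = 33 events, and entry reason would overlap with respiratory rate and saturation, which help to define worsening. This limits the number of covariates; it does not argue against having any.

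Finally, the predictive model of ventilation failure could include mode, but the plan does not say so, nor does it present that model as estimating the CPAP versus BiPAP effect. It does not fill the gap.

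**Conclusion.** The concern holds as a loss of precision, not as a bias. The plan tests its only randomised contrast without adjustment, although it collects suitable covariates on the last OHF day. For continuous outcomes the variance saved is 9%, 25% or 49% at assumed correlations of 0.3, 0.5 or 0.7. For binary failure the saving is about 10% to 26% in the simulated scenarios, with power gains of 2.4 to 4.4 points at 40 per arm and 6.0 to 10.8 points at 80. All of this depends on how prognostic the pre-ventilation values are, which the documents do not say. The change is worth making because it needs little new data and alters no treatment. It does not make up for the absence of a stated primary endpoint and sample size.

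**What to change.** In the statistics section, replace the sentence that carries the general tests over to CPAP versus BiPAP with a pre-specified analysis of all patients as randomised:

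- **Continuous outcomes:** a linear model with arm and the last value of the same variable recorded before randomisation. For blood gases, use the most recent OHF gas.
- **Failure of ventilation:** logistic regression with arm and one or two covariates fixed in advance, for example last-OHF-day respiratory rate and FiO2. Report a standardised risk difference. Name this measure in the plan, because adjusted and unadjusted odds ratios are different quantities.
- **Reporting:** give the unadjusted result alongside.
- **Reason for leaving OHF:** include it as a covariate only if it is recorded, stating how a patient who meets both criteria is classified and keeping the total number of covariates small.
- **Missing or old pre-ventilation values:** state in advance how they are handled.

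The cost is a few lines of plan text, slightly more analysis work, a rule for missing or older values, and possibly one added case-report-form field for the reason. No clinical procedure changes.

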#### **Day 2**

24h after starting non-invasive ventilation a new arterial blood gas analyses and record clinical parameters will be performed. If the therapy parameters have been modified it will also be recorded.

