#### **Day 3**

48h after starting non-invasive ventilation control includes arterial gasometry, blood analyses and record clinical parameters and vital constants specifying ventilation parameters.

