#### **Completion criteria to treatment with CPAP/BiPAP:**

- Respiratory improvement that it leaves to change a conventional oxygen system or OHF.
- Lack of tolerance of non-invasive ventilation.
- Worsening of respiratory failure defined by PaO2/FiO2 < 100, 20% increase from baseline (if basal pCO2 > 40 mmHg), sustained signs of distress, SaO2 < 90% or Glasgow < 15, in patients without non-intubation orders.
- Death of the patient.

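### The Day 1 controls on non-invasive ventilation are timed from the start of high flow, while the 24 h and 48 h controls are timed from the start of ventilation

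*Combined protocol and SAP*

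**What the plan says.** In the section on non-invasive ventilation, under Interventional group, Day 1, arterial gases and vital signs "will be performed at 1h, 4h, 6h and 12h after starting high flow therapy specifying ventilation parameters".

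The next two controls of the same phase use a different origin. Day 2: "24h after starting non-invasive ventilation a new arterial blood gas analyses and record clinical parameters will be performed". Day 3: "48h after starting non-invasive ventilation control includes arterial gasometry".

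The section on standard support with OHF has a nearly identical Day 1 sentence: "Arterial blood gas analyses and record of vital constants will be performed at 1h, 4h, 6h and 12h after starting high flow therapy". Its Day 2 control also runs from the start of OHF: "24h after starting high flow therapy a new arterial blood gas analyses and record clinical parameters will be performed".

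The statistical section analyses gases and vital signs at each control, first for patients in whom OHF did not fail against the NIV group. It then adds: "The same analyses are performed between the CPAP and BIPAP treatment subgroup".

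**The concern.** Patients reach NIV, and are randomised to CPAP or BiPAP, only after intolerance of OHF or worsening on it. The start of OHF therefore always precedes the start of NIV, by an interval that varies between patients. A Day 1 NIV schedule counted from the start of OHF does not measure time on the randomised treatment.

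If the case report form or the analyst follows the text as written, a control labelled 12 h stands for a different length of NIV in each patient. In some patients it is a measurement taken before NIV began. CPAP versus BiPAP is the randomised comparison, and Day 1 is when pressure and FiO2 are titrated, so the early gas response is where a common clock matters most. Mixing exposures, and mixing pre-treatment with on-treatment values, blurs any early difference between the modes.

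**Working it through.** **Inputs.** As written, the Day 1 NIV controls are at c = 1, 4, 6 and 12 h from the start of OHF (NIV section, Day 1). The following NIV controls are at 24 h and 48 h from the start of NIV (Days 2 and 3). The protocol gives no switch time, so let h be the hours on OHF at the switch; the values of h below are illustrative. Randomisation is taken to coincide with the switch. The plan states no figure to reproduce.

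**Which origin was meant.** The NIV Day 1 sentence matches the OHF Day 1 sentence word for word up to the naming of high flow, then adds a request for ventilation parameters. These exist only once the patient is on NIV. The sentence sits under the NIV heading and leads into two controls counted from the start of NIV. Carry-over from the OHF section is an inference, but a strong one.

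**Consequence of the literal text.** A control at c falls c − h hours after the start of NIV, and before NIV if c < h. Controls on NIV are those with c > h:

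- h < 1: 4 controls
- 1 ≤ h < 4: 3
- 4 ≤ h < 6: 2
- 6 ≤ h < 12: 1
- h ≥ 12: 0

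For h < 12 the last Day 1 control falls at 12 − h hours on NIV and the next scheduled gas at 24 h. The longest interval on NIV without a scheduled gas in the first 24 h is therefore 24 − (12 − h) = 12 + h hours. For h ≥ 12 it is 24 h.

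| h (hours on OHF) | Day 1 controls on NIV, hours since NIV start | Longest interval without a scheduled gas, first 24 h |
|---|---|---|
| 0.5 | 0.5, 3.5, 5.5, 11.5 | 12.5 h |
| 2 | 2, 4, 10 | 14 h |
| 5 | 1, 7 | 17 h |
| 8 | 4 | 20 h |
| 11 | 1 | 23 h |
| 12 or more | none | 24 h |
| Counted from NIV start instead | 1, 4, 6, 12 | 12 h |

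In the last row the gaps up to 24 h are 1, 3, 2, 6 and 12 h. For two patients who switch at h = 2 and h = 8, the control labelled 12 h falls at 12 − 2 = 10 h and 12 − 8 = 4 h on NIV, 6 h apart under one label.

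**Can h exceed 12?** The OHF section schedules controls at 24 h and 48 h of OHF, so longer OHF is foreseen. Those controls also serve patients who succeed on OHF, so they do not show how often a switch comes after 12 h.

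**Safety.** The criteria for worsening on NIV begin: "Worsening of respiratory failure defined by PaO 2 /FiO 2 < 100, 20% increase from baseline". PaO2/FiO2 needs an arterial gas. So does the 20% rise if it refers to pCO2, which is the likely reading, although the text does not say what rises. The other three criteria (distress, SaO2 below 90%, Glasgow below 15) need no gas. Respiratory rate, SaO2 and other vital signs "start to be monitored continuously" from admission.

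**The case against.** The strongest reply is that this is a slip the document resolves by itself. The heading, the request for ventilation parameters and the Day 2 and Day 3 wording all point to the start of NIV, and on that reading no defect remains. Staff could not follow the literal text for a control that precedes NIV, so they would meet the contradiction early. No number of affected patients can be given, nothing shows that the literal clock was used, and no named endpoint is tied to a Day 1 control.

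Much of this stands. It bears on how much harm is likely, and it makes this an inconsistency rather than a deliberate design choice. It does not make the rule correct. For an early switch such as h = 2, three of the four controls can be taken on the literal clock with ventilation parameters recorded, so the error could pass unnoticed. The analysis section relies on the controls without restating their origin, so a reader there has nothing to correct the text with.

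**Conclusion.** The concern holds: the operative Day 1 NIV schedule names the wrong time origin and conflicts with Days 2 and 3 of the same phase. Followed literally, between none and all four of the Day 1 controls precede NIV, depending on time on OHF, and those that remain fall at unequal NIV exposures. The mismatch in the text is certain. That the start of NIV was meant is an inference, though a well-supported one. The practical effect depends on switch times and on what the case report form says, and the protocol gives neither. The wording is the same for both arms, so it blurs the CPAP versus BiPAP comparison rather than favouring one mode. The problem is mainly the timing of the early gas comparisons, not patient surveillance. It should be corrected.

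**What to change.** In the NIV section, Interventional group, Day 1, name the start of non-invasive ventilation as the origin for the 1, 4, 6 and 12 h controls. The NIV series then runs at 1, 4, 6, 12, 24 and 48 h on one clock, mirroring the OHF series. State in the statistical section that all NIV-phase controls in the CPAP versus BiPAP analyses are indexed by time since the start of NIV.

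The cost is a few words in the protocol and a check of the case report form; no controls are added. If any patients were followed on the literal clock, relabel their Day 1 controls by actual time since the start of NIV and treat values taken before it as pre-NIV measurements.

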#### **Day 2**

24h after starting non-invasive ventilation a new arterial blood gas analyses and record clinical parameters will be performed. If the therapy parameters have been modified it will also be recorded.

#### **Day 3**

48h after starting non-invasive ventilation control includes arterial gasometry, blood analyses and record clinical parameters and vital constants specifying ventilation parameters.

#### **Last day of therapy**

Control includes blood analyses and record clinical parameters, vital constants and ventilation parameters.

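### The last-day-of-therapy control is timed by how NIV ends, so testing CPAP against BiPAP there can turn a difference in duration or stopping reason into an apparent, or hidden, marker effect

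*Combined protocol and SAP*

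**What the plan says.** Most NIV controls are tied to a number of hours. Day 1 of the NIV section sets controls at 1, 4, 6 and 12 h. Day 2 reads "24h after starting non-invasive ventilation a new arterial blood gas analyses and record clinical parameters will be performed", and Day 3 reads "48h after starting non-invasive ventilation control includes arterial gasometry, blood analyses and record clinical parameters and vital constants specifying ventilation parameters".

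The final NIV control, under Last day of therapy, has content but no time: "Control includes blood analyses and record clinical parameters, vital constants and ventilation parameters". Its timing therefore comes from the completion criteria for CPAP/BiPAP, which list four ways for NIV to end:

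- "Respiratory improvement that it leaves to change a conventional oxygen system or OHF"
- "Lack of tolerance of non-invasive ventilation"
- "Worsening of respiratory failure defined by" a set of criteria that includes SaO2 and signs of distress
- "Death of the patient"

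The statistics section says that "analytical, blood gas variables and vital signs are analysed in each of the controls", and that the same analyses are made between CPAP and BiPAP. It does not exclude the last-day control, adjust for length of treatment or separate patients by reason for stopping. Its regression models are for predicting failure of high flow and of NIV, not for these comparisons.

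**The concern.** CPAP against BiPAP is the only randomised comparison in the trial. At the last-day control one patient may be measured hours after randomisation, because the mask was not tolerated, and another many days later, after recovery. The arms are then compared at unequal times, and the outcome chooses the time.

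This can mislead in two ways.

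- **Unequal time.** A blood marker that changes over days will differ at the last day if NIV lasts longer in one arm, even if mode does nothing to the marker's course.
- **Mixture.** SaO2 and distress are among the stopping criteria, so last-day vital signs partly restate why NIV stopped. A different share of failures shifts the mean. Because the stopping rule partly fixes the value, a real difference can also be masked.

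This is separate from the question of who is still on NIV at 24 or 48 h; it would remain with a complete last-day record for everyone. For blood analyses the weight is considerable: after NIV starts they are scheduled only at 48 h and on the last day, so one of the two scheduled comparisons is affected. Vital signs have several fixed-time controls besides.

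**Working it through.** The plan has no figure of its own to reproduce: it states no sample size, significance level, NIV duration, named blood marker or marker trend. Every input below is an assumption, used only to show how the mechanism behaves.

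**1. Unequal time: inputs.** Same log-linear path in both arms, falling 15% a day (slope ln 0.85 = -0.1625 per day). Between-patient SD 0.8 on the log scale. Gamma-distributed NIV duration with shape 2.5, mean 4 days in one arm and 6 in the other. Two-sample t-test on the log last-day value, two-sided 0.05.

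**2. Expected shift.** Slope × difference in mean duration = -0.1625 × 2 = -0.325, a geometric mean ratio of 0.85² = 0.72.

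**3. Check by hand at 60 per arm.**
- Variance of duration = mean²/2.5: 16/2.5 = 6.4 and 36/2.5 = 14.4.
- Variance of the last-day value = 0.64 + 0.0264 × variance of duration: 0.64 + 0.169 = 0.809 and 0.64 + 0.380 = 1.020.
- Standard error = √((0.809 + 1.020)/60) = 0.175.
- 0.325/0.175 = 1.86, so the chance of p < 0.05 is about Φ(1.86 - 1.96) = Φ(-0.10) = 46%.

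**4. Simulation of the same model.** Results vary by about a percentage point between runs.

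| Setting | Per arm | Share with p < 0.05 |
|---|---|---|
| 4 vs 6 days | 20 | about 17% |
| 4 vs 6 days | 40 | about 33% |
| 4 vs 6 days | 60 | about 45% |
| 4 vs 5 days | 20 | about 8% |
| 4 vs 4 days | 60 | about 5% |

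A rank test, which the plan also allows, gives about 42% at 60 per arm for 4 vs 6 days.

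**5. Not every marker improves.** Step 1 lets the marker fall even in patients who stop for worsening or death. Suppose instead that 40% in each arm fail, with 4 vs 6 days and 60 per arm.
- Failures flat: shift = 0.6 × (-0.325) = -0.195, ratio 0.82; p < 0.05 in about 18% of trials.
- Failures rising 10% a day: shift = -0.195 + 0.4 × 2 × ln 1.10 = -0.195 + 0.076 = -0.119, ratio 0.89; p < 0.05 in about 8% to 9%.

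**6. Fixed time as comparison.** A second model had total SD of about 1, trends of 0 to 0.2 SD a day, durations differing by 0 to 3 days and 20 to 60 per arm. The 48 h test rejected in 4.2% to 5.9% of trials in every setting. Where there was both a trend and a difference in duration, the last-day test rejected in 6.4% to 73.0%. That model gives every patient a 48 h value, which the plan does not guarantee.

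**7. Mixture.** Take mean SaO2 at stopping as 96% if improved and 88% if failed. The difference between arms is 8 points × the difference in failure share: 40% vs 50% gives 8 × 0.10 = 0.8 points, and 40% vs 60% gives 8 × 0.20 = 1.6 points. Patients with the same outcome do not differ at all.

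**The case against.** The best counter-argument is that duration is itself a result of the randomised mode. If mode changes how long NIV lasts, a last-day difference is a genuine consequence of assignment; if mode changes nothing, the durations agree in expectation and the test is valid. This stands. A reader might take the 45% as an inflated type I error rate for the randomised comparison. It is not one: with equal durations the rate is about 5%. What goes wrong is the label, an effect on duration read as an effect on the marker.

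It also stands that the larger percentages need favourable assumptions. They shrink with fewer patients, with a smaller gap in duration, and once failing patients' markers do not fall. The documents support neither the inputs nor a claim that such a difference will occur in this trial.

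The statistics section does not name the last-day visit. Its inclusion follows from the reference to every control together with the protocol's own use of that word for the visit. That is the plain reading, but it is an inference.

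Finally, the statistics section names no primary endpoint, and nothing shows that a trial conclusion rests on last-day values. That limits the weight of the point but does not make the last-day test interpretable.

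**Conclusion.** The point holds in conditional form. As written, the plan tests the randomised arms at a time chosen by the outcome. A difference in NIV duration or in stopping reasons can then appear as a laboratory or vital-sign effect, or conceal one; without such a difference the test behaves properly. The size cannot be fixed from the documents: in the duration model the share of trials with p < 0.05 runs from nominal to about 45% at 60 per arm.

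Two wider readings are not supported. One is that the whole between-arm comparison is compromised: the problem is confined to the last-day control, and the one-in-two count applies only to scheduled blood analyses after NIV starts. The other is that blood gases are equally affected: the last-day control does not list arterial gasometry.

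The change is worth making because it is cheap and removes an ambiguity from the randomised comparison.

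**What to change.** In the statistics section:

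- Restrict between-arm tests of laboratory values and vital signs to the fixed-time controls, with laboratory values compared at 48 h.
- Report how many patients in each arm stopped NIV before 48 h, and use their 48 h values where these exist. The 48 h control is written as part of NIV, and no sample is specified for patients who have already stopped, so the 48 h comparison has its own selection problem and should show it.
- Present last-day values descriptively, by reason for stopping.
- Compare time from randomisation to end of NIV between arms as cumulative incidence by reason (improvement, intolerance, worsening, death).

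The completion criteria need no change for this purpose; their four categories serve as the reasons.

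Cost: mainly wording, but not wholly. The reason for stopping is not among the items listed for the last-day record, so the plan should say that it is recorded. There is one fewer tested time point, and patients who stop before 48 h may have no tested laboratory value.
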